## 7.0 Multi-Site Research Communication

To facilitate communication, we have budgeted for face-to-face meetings of the PIs and the larger team and will include site-specific investigators at each of the local meetings. We hold weekly lab meetings and monthly conference calls across sites for all investigators to review recruitment progress, assessment issues, and discuss publications. Other informal conferencing occurs between the PIs, who routinely speak at least weekly and much more frequently by electronic means. This organizational structure has been in place for the past 5 years and functions efficiently and without major difficulties. We have collaborated for many years and conflicts have not arisen. Should a conflict arise, [name] has final say on administrative and fiscal issues, and on issues related to treatment development. [name] has final say on issues related to his budget components (e.g., staffing) and issues related to technology development and adaptation. In the unlikely event that the PIs are unable to resolve an issue, it would be put forward for discussion with the investigative team and a vote would be taken among the 9 participants. [name] and [name] would accede to the voting results. In the unlikely event that the investigative team cannot resolve the issue, it will be referred to the Data Safety and Monitoring Board (DSMB) who will review the matter and determine an equitable and binding decision. The full DSMB plan is located on page 25 of the grant under the heading, "Data and Safety Monitoring Plan".

The UH study team, under the supervision of the contact PI, will provide services to:

- Coordinate communications with partnering sites
- Request and receive information and documentation from partnering sites
- Develop template materials for review by the UH IRB and for limited modification by participating sites
- Submit materials from all sites to the UH IRB and coordinate responses to any IRB queries
- Provide documentation to participating sites

Participating sites will follow local procedures to coordinate, collect and verify information such as:

- Local context
- Site variations in areas such as recruiting, informed consent, HIPAA, populations
- Conflict of Interest disclosure and management
- Completion of ancillary reviews

**FULL PROTOCOL TITLE:** Mobile Health to Monitor Risk for COVID-19 and Improve Mental Health during the Pandemic

- Training and qualifications of study team
- Continuing Review or Closure information
- Reportable Events

The contact PI will maintain a copy of this communication plan and any other communication plans that are developed. Copies will be made available to the participating sites as appropriate.

Before initiating the study, each participating site will execute a reliance agreement with the IRB which will clarify the roles and responsibilities of the sIRB and the site.

The Insight app encrypts all data as it is collected. This data is synced with Azure servers up to four times per day. Study data are available through Insight's encrypted web portal (i.e., the content management system). Each individual member of the research team has a STRONG password. Only team members that require access to study data will be granted the ability download data directly to their encrypted university computer. Given both sites are able to download study data directly, there is not a need to transmit it across study sites. Research data will be encrypted and saved to the study phones or through REDCap.

As required by NIH, we will provide de-identified data from this project to interested individuals one year following achievement of the aims of the project (i.e., publication of the main outcome papers). These data will be provided in digital format (i.e., disk) with clear labels for all variables. Data will be de-identified and released directly by the investigators that provide evidence of their institutional IRB approval for planned analyses of the data. Our team will be available to address queries.

## 8.0 Study Timelines

The present study will include a baseline assessment, a 3-month intervention period, a 3-month continued assessment period (with access to intervention materials), and 3- and 6-month post-baseline assessments that includes a qualitative interview for selected participants via phone or online platform (e.g., Zoom). The qualitative interviews will be recorded and securely stored for qualitative analysis (or completed by the participant via REDCap survey if a medical condition prevents them from being able to speak for long periods of time). Recordings will be transcribed by internal staff, Microsoft Transcribe, or by approved contractors. When using Microsoft Transcribe, all transcriptions will be reviewed by study staff. Hence, the total duration of an individual subject's participation in the study will be 6 months. We expect each study appointment will take approximately 30-60 minutes to complete.

Baseline timeline: All study assessments as well as all EMAs will be conducted remotely through the Insight app. Participants who do not have a mobile phone will be mailed one. The Insight™ app will be downloaded and activated during the baseline session using a unique activation code provided by the research team. All interactions with the Insight and EASE app will be date, time, and Geolocation (GPS) stamped and app feature use will be recorded for future analysis. After downloading the Insight app, participants will use the app to complete the baseline assessment. We expect participants will take approximately 30-minutes to complete all baseline assessment measures (please refer to section 10.0 procedures involved for a detailed list of measures participants will be prompted to complete). Following completion of the baseline assessment, the

**FULL PROTOCOL TITLE:** Mobile Health to Monitor Risk for COVID-19 and Improve Mental Health during the Pandemic

app will request a code. This code will be used to ensure that the participant is placed in their randomly assigned study condition (EASE or Control). Upon entering this code, the app will automatically begin prompting twice daily EMAs for 6-months (please refer to section 10 below and Table 3 for a list of EMA assessments and more detailed information).

**Follow-up timeline:** Participants will complete follow-up assessments at 3- and 6-months following the baseline assessment, which will also be completed using the Insight app, in the same manner as the baseline assessment. Assessments to be conducted have been detailed below (please see 10.0 procedures involved). We expect the 3- and 6-month follow up assessment sessions will each take participants approximately 30 minutes to complete. Moreover, during the time between the baseline and 6-month follow-up assessments (6-month continuous assessment period) participants will continue to receive daily EMAs and will have access to all intervention materials included in the app.

**Project Timeline.** Year 1 will focus on obtaining IRB approval (i.e., submit application, respond to reviewers, and re-submit), hiring and training research staff, and beginning the enrollment. Year 2 will focus on recruitment, enrollment, and collecting follow-up data. Year 3 will focus on collecting follow-up data, data cleaning/analysis, and manuscript preparation and dissemination, including presenting findings at professional conferences and community-based events. For the present study, we expect approximately 50% of participants who click on our advertisement to be eligible; 75% of those who complete the phone screener to be eligible; and 95% of those to consent to participate. Weighted compensation schedule and reminder calls will be utilized to minimize subject dropout. Based on our ongoing work, we expect to enroll 39 participants each month, on average, across the 21-month enrollment period. We expect to retain 80-90% of subjects at each follow-up assessment points.

Project Timeline

ACTIVITIES TO BE COMPLETED	Year 1				Year 2				Year 3			
	Q1	Q2	Q3	Q4	Q1	Q2	Q3	Q4	Q1	Q2	Q3	Q4
HIRING AND TRAINING STAFF; STUDY PREPARATION	•											
IRB SUBMISSION AND APPROVAL	•											
ENROLLMENT AND ADMINISTER STUDY PROCEDURES		•	•	•	•	•	•	•	•	•		
DATA CLEANING									•	•		
DATA ANALYSIS & DISSEMINATION									•	•	•	•

Q1: Months 1-3, Q2: Months 4-6, Q3: Months 7-9, Q4: Months 10-12. *Study Implementation (Year 1):* Staff hiring and training; IRB submission; and recruitment preparation. *Enrollment and Study Procedures (Years 1-3):* Recruitment; screening; enrollment; assessment; and follow-up. *Data Cleaning and Dissemination (Years 3):* Collect follow-up data; data cleaning and merging, analysis, and interpretation; research dissemination preparation; and manuscript preparation.

## 9.0 Study Endpoints

The primary study endpoint will be recruitment of all study subjects at the end of the study enrollment period. The secondary study endpoint will be the collection of study data from all participants following the 6-month follow-up.

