## 1.0 Objectives

1.1 The proposed research is directly relevant to public health because it aims to target health disparities in access to behavioral health care during the COVID-19 pandemic among Black, Hispanic, and American Indian (BLAI) individuals via testing an adaptation of an established, initially validated, low-cost, mobile application ('app') designed to reduce ongoing mental health concerns among BLAI individuals with elevated anxiety and/or depressive symptoms (Easing Anxiety Sensitivity for Everyone [EASE] App). Using a precision medicine approach, EASE targets anxiety sensitivity, a transdiagnostic individual difference factor implicated in the etiology, maintenance, and progression of anxiety and depressive symptoms. EASE includes COVID-19 symptom monitoring, exposure management skills, and psychoeducation on COVID-19-related stress and the impact of stress on susceptibility to infection and disease progression; if successful, this study will provide evidence that the EASE app-based intervention can address the public health concerns of anxiety and depressive symptoms among BLAI during the COVID-19 crisis. **Aim 1.** To compare the effect of EASE with COVID-19 specific elements (n = 420) to a standard-of-care digital intervention with educational material covering stress reduction, and anxiety and depression symptom management and COVID-19 specific elements (n = 420). To evaluate the efficacy of the experimental intervention across each race/ethnic group. **Aim 2.** To identify the therapeutic mechanisms of EASE, including theoretically driven mediators (i.e., anxiety sensitivity, subsequent changes in COVID-19 related stress and fear) and moderators (i.e., perceived racial discrimination, social support, and socioeconomic status).

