1.2 **H1:** Those assigned to EASE will show greater reductions in anxiety and depression symptoms, and greater reductions in functional impairment in daily responsibilities (e.g., work performance, household maintenance, and social interactions, and relationships) relative to the control group. **H2:** Effectiveness of EASE will be similar across racial/ethnic groups. **H3:** Intervention effects on study outcomes will be mediated by reductions in anxiety sensitivity and changes in COVID-19 related stress and fear. **H4:** Perceived discrimination (worse intervention outcomes), social support (better intervention outcomes), and socioeconomic status (SES; lower SES associated with worse outcomes) will be examined as potential moderators of the EASE effects.

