Data analysis overview: Hypotheses for Aims 1 and 2 will be examined using latent growth models (LGM), multilevel structural equation models (MSEM) and latent difference score models using MPlus 8.0. To simplify subsequent sections, an overview of the common data analysis elements is presented first. Data will first be examined for multivariate normality and outliers to determine the most appropriate estimator. The maximum likelihood (ML) estimator will be used if data are approximately normal. Robust maximum likelihood (MLR) will be used if the data are not multivariate normal. We anticipate some participant attrition during the trial. Missing data will be handled in all analyses using direct ML techniques within MPlus under a missing at random (MAR) assumption. Modern missing data techniques such as direct ML increase statistical power and provide more accurate estimates of model parameters and standard errors and are the recommended intent-to-treat approach for clinical trials. LGM will generally be used to model outcomes collected at major assessments. MSEM will be used to further examine the longitudinal course of outcomes and hypothesized mechanisms of action as MSEM is ideally suited for disentangling within and between individual variance in order to more precisely estimate main effects, lagged effects, and indirect effects in intensive longitudinal designs. Evaluation of model fit in the LGM/MSEM models will be examined using fit diagnostics (i.e., standardized residuals) and common fit statistics (i.e., root mean square error of approximation) following the associated cutoff criteria recommended by Hu & Bentler. We will assess the equivalence of the treatment groups on key baseline

**FULL PROTOCOL TITLE:** Mobile Health to Monitor Risk for COVID-19 and Improve Mental Health during the Pandemic

variables (demographics and psychological variables); variables on which the groups differ will be used as covariates in the final analyses. We will also examine attrition from the study as a dichotomous outcome and use logistic regression to determine if treatment assignment predicts attrition.

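### Section 9.0 names recruitment and data collection as the endpoints, and these documents do not designate H1's primary outcome, visit, tested parameter, alpha or success rule

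*Combined protocol and SAP*

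**What the plan says.** Section 9.0 has two sentences: "The primary study endpoint will be recruitment of all study subjects at the end of the study enrollment period", and "The secondary study endpoint will be the collection of study data from all participants following the 6-month follow-up".

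The purpose of the trial is set out in Section 1.0. Aim 1 is "To compare the effect of EASE with COVID-19 specific elements" against a standard-of-care digital control. H1 is directional: "Those assigned to EASE will show greater reductions in anxiety and depression symptoms, and greater reductions in functional impairment in daily responsibilities".

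Other sections supply parts of an efficacy analysis:

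- Table 3 (Section 10.0) tags four measures to H1: OASIS, ODSIS, the Sheehan Disability Scale (SDS) and Daily Activities.
- Section 10.0 places follow-up at 3 months (end of treatment) and 6 months. OASIS and ODSIS are also collected in the weekly Sunday diary.
- The analysis overview in Section 20.0 lists latent growth models (LGM), multilevel structural equation models (MSEM) and latent difference score models for Aims 1 and 2. It then says "LGM will generally be used to model outcomes collected at major assessments" and "MSEM will be used to further examine the longitudinal course of outcomes and hypothesized mechanisms of action".
- The overview covers estimator choice, missing data under MAR, model fit and baseline covariates. It announces further detail ("To simplify subsequent sections, an overview of the common data analysis elements is presented first"), but the next section is 21.0, on sharing results with participants.

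**The concern.** A recruitment target can be met or missed whatever EASE does, and so can a data-collection target. A trial that met both stated endpoints would have established nothing about Aim 1.

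The rest of the text does not repair this. It offers four tagged measures, two visits and more than one model, without saying which combination decides H1. Two analysts who both followed Section 20.0 faithfully could reach different conclusions about H1. The choice between them could also be made after the results are known. That choice affects both the risk of a false claim and the chance of detecting a real effect.

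**Working it through.** **1. What is designated and what is not**

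| Element needed for H1 | Stated? |
|---|---|
| Comparison and direction | Yes, Section 1.0 |
| Candidate measures | Yes, four tagged in Table 3; none ranked |
| Visits | Yes, 3 and 6 months; neither named as deciding |
| Model | In part: LGM generally for major assessments, MSEM to look further |
| Growth form and tested parameter | No |
| Alpha and sidedness | No |
| Any-one or all-must-succeed rule, multiplicity | No |

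**2. The plan's own figure.** Section 5.0 gives 880 randomized: 4 × 220 = 880 and 2 × 440 = 880. This adds up, but it cannot be derived from a power calculation, because no alpha, power, effect size or SD is given. Section 1.0 has 420 per arm instead (840 in total).

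**3. Inputs for the illustration.** From the documents: 440 per arm (Section 5.0), and retention of 80-90% (Section 8.0), so the low end is 0.8 × 440 = 352. Assumed: two-sided 5% tests, equal correlation ρ of 0.5 to 0.9 between test statistics, and a true effect of 0.20 SD on every measure. These are two-mean approximations, not the planned models.

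Write each statistic as Z = μ + √ρ·U + √(1−ρ)·E, with U and E independent standard normal and μ = d/√(2/n). Only results in EASE's favour count, because H1 is directional.

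- P(any of k) = 1 − ∫ φ(u) Φ((1.96 − μ − √ρ·u)/√(1−ρ))^k du
- P(all k) = ∫ φ(u) Φ((μ − 1.96 + √ρ·u)/√(1−ρ))^k du

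**4. False support for H1 under an any-one rule (μ = 0)**

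| Tests | ρ = 0.5 | ρ = 0.9 |
|---|---|---|
| 1 | 2.5% | 2.5% |
| 3 (one per H1 domain) | 6.3% | 4.2% |
| 4 (one per tagged measure) | 7.8% | 4.7% |
| 6 (3 × 2 visits) | 10.4% | 5.4% |
| 8 (4 × 2 visits) | 12.5% | 6.0% |

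If all of 3 or 4 measures must succeed, the corresponding rate is at most about 1.1%.

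**5. Chance that H1 is met at a true 0.20 SD**

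μ = 0.20/√(2/440) = 2.97, or 0.20/√(2/352) = 2.65.

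| Per arm | Measures | Any one (ρ = 0.5, 0.9) | All (ρ = 0.5, 0.9) |
|---|---|---|---|
| 440 | 3 | 97%, 90% | 68%, 78% |
| 440 | 4 | 98%, 91% | 63%, 76% |
| 352 | 3 | 93%, 84% | 55%, 67% |
| 352 | 4 | 95%, 85% | 49%, 65% |

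For the same data and the same true effect, the unstated rule moves the chance of supporting H1 from 49-78% to 84-98%.

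**The case against.** **Section 9.0 may be a milestone field in an institutional template.** That is plausible, and it would explain the wording. But no other section designates an efficacy endpoint, so the explanation does not fill the gap.

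**The plan does have efficacy outcomes and models.** This stands. A reader might infer that no efficacy analysis is planned, or that MSEM is an unassigned rival to LGM. The documents do not support either reading: Table 3 tags four measures to H1, and Section 20.0 gives LGM the major assessments and MSEM a follow-on role. What remains is narrower. The LGM assignment is qualified by a loose adverb, no parameter is named, and nothing says whether a Sunday-diary MSEM result could itself support H1.

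**The wording of H1 joins its outcomes with a conjunction, so perhaps all must succeed.** If so, false-positive inflation disappears. The visit, the parameter, the alpha and the impairment measure that counts (SDS or Daily Activities) would still be open, and the lower power in step 5 would apply.

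**The error rates could be stated more alarmingly.** Counting significant results in either direction gives 8-16% for 3-4 tests and 11-25% for 6-8. A result favouring control cannot support H1, so those figures overstate the risk about twofold. Nor do the documents adopt an any-one rule.

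**A linear growth model might distort the 3-month effect.** The growth form is not stated, and the size of any distortion depends on how the arm effect at baseline is handled. No figure can be attached from these documents.

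**The rule may exist elsewhere.** Section 7.0 points to the grant, and the overview refers to sections that do not follow. The supportable statement is that the rule is absent from these documents, not that it was never written.

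**Conclusion.** The point stands, and it should be fixed before outcome data by arm are examined. Its core is textual and rests on no assumption: the stated primary and secondary endpoints cannot answer Aim 1 or H1, and no other section here designates the outcome, visit, parameter, alpha or success rule.

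Its size can only be illustrated. Under the assumptions in the working, an any-one rule raises the chance of false support for H1 from 2.5% to roughly 4-8% (3-4 tests) or 5-12.5% (6-8 tests). An all-must-succeed rule does not inflate error but lowers the chance of success substantially. The criticism is that the choice is open, not that either rule is wrong.

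**What to change.** Before outcome data by arm are examined:

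1. **Section 9.0.** Replace both endpoints with participant-level ones from measures already collected. One example is the EASE-control difference in change from baseline to 3 months in OASIS and in ODSIS. Relabel recruitment and data completeness as feasibility metrics.
2. **Section 20.0, parameter.** Name what is tested, for example the arm effect on 0-3 month change in the latent difference score model already listed.
3. **Section 20.0, decision rule.** State the alpha and one success rule with multiplicity control, for example Holm across the two measures at two-sided 5%.
4. **Everything else.** Make the remaining H1 measures, the other visit and the Sunday-diary MSEM analyses secondary, so that they are not routes to an H1 claim.

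The 3-month visit, the pair of measures and Holm are examples. The sponsor may fix another outcome, visit or rule, provided it is written in advance. If SDS is part of the rule, reconcile its item count first: Section 10.0 describes 5 items and Table 3 lists 4.

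**Cost.** No new data collection; amended text and any approval the amendment requires. There is a modest loss of sensitivity. The 80%-power detectable effect is (z + 0.842)·√(2/n), with z = 1.960 for a single 5% test and 2.241 for Holm's first step at 2.5%:

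- 440 per arm: 2.802 × 0.0674 = 0.19 SD, rising to 3.083 × 0.0674 = 0.21 SD.
- 352 per arm: 2.802 × 0.0754 = 0.21 SD, rising to 3.083 × 0.0754 = 0.23 SD.

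If SDS must also succeed at 5% after both symptom measures pass Holm, simulated power for full H1 at a true 0.20 SD is about 51-76% across 336-440 per arm (336 = 0.8 × the 420 in Section 1.0) and ρ of 0.5 to 0.9. The sponsor should weigh that before making function part of the primary claim.

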## 10.0 Procedures Involved

All study data (both survey data and EMAs) will be collected through the Insight app which participants will be asked to download during their baseline assessment, with the only exception being the study screener, consent process, and qualitative follow-up interviews for selected participants which will be completed through REDCap and phone call. Qualitative interviews will

**FULL PROTOCOL TITLE:** Mobile Health to Monitor Risk for COVID-19 and Improve Mental Health during the Pandemic

be recorded and transcribed for analysis. All data being collected from research participants will be input into the Insight app by participants themselves.

Participants will be recruited online via social media and internet outlet (e.g. Craigslist, Facebook) advertisements that target residents of the United States. Individuals who click our ads will read the study description and complete a brief study screener in REDCap. Participants will also be recruited through Qualtrics Panels Recruitment which will gather basic demographic information to assess eligibility. Also, we will be recruiting American Indian participants through BuildClinical. BuildClinical is a data-driven platform that helps academic researchers recruit participants for research studies more efficiently using social media, software, and machine learning. BuildClinical will direct individuals to their own platform where they will receive more information about the study. They will also be able to take our pre-screener survey through BuildClinical and we will be able to download a list of pre-eligible participants. This program will have access to the following information: (1) Full name, (2) Phone number, (3) Phone number (secondary), (4) Email address, (5) Age, (6) Date of birth, (7) Ethnicity, (8) Race, and (9) Gender assigned at birth. BuildClinical does not interact with data outside of sending the data to the University of Houston. BuildClinical's Secure Socket Layer (SSL) software encrypts all inputted information and keeps the information private and compliant. BuildClinical will create all recruitment materials for use on their platform once recruitment through BuildClinical is approved by the University of Houston Institutional Review Board. Additionally, participants will be recruited via university and online LISTSERV services. Those who initially meet the study inclusion criteria will complete a phone call with study staff within one week of completing the REDCap screener. During this call, study staff will verify that individuals meet the study inclusion criteria, staff will review study details with each individual; and interested individuals will complete the informed consent process (signatures will be collected digitally via REDCap) and begin the screening assessment. Participants who are found to be eligible during the screening process will then be instructed to download the INSIGHT app onto their smartphone to complete the Baseline assessment. If a participant requires a study phone, they will be mailed one and scheduled to complete the baseline assessment once the phone has been received. Participants who report they are not the only users of their phone will be mailed a study phone for the study.
